#### 2.6.4 Supportive analyses

[figure not shown]
Sensitivity analyses and supplementary analyses will be conducted in order to provide evidence that the results seen from the key secondary objectives are robust.

For the change from baseline in mSASSS at Week 104 a sensitivity analyses will be conducted to determine the impact of missing data handling on the primary estimand by changing the covariates in the imputation model (e.g., using different ways of adjusting for baseline mSASSS, adding additional covariates). Additional supplementary analyses may be conducted to examine different estimands which are also deemed clinically relevant, such as the estimand based on the hypothetical strategy which would examine the treatment effect in outcomes where biologic rescue was not available to subjects. In this case the data after the occurrence of the intercurrent event would be imputed under the MAR assumption.

For the proportion of subjects with absence of new syndesmophyte at Week 104 the same sensitivity and supplementary analyses used in the primary objective will be done.

The effect of the COVID-19 pandemic on the study will be monitored and assessed. An additional supportive analysis related to its effect may be performed as described in [Section 2.15](#).

## **2.8 Safety analyses**

Safety analyses will be performed on-treatment received or actual treatment as described below:

The actual treatment or treatment received for summaries of safety data will differ to the treatment assigned at randomization only if a subject received the wrong treatment during the entire study.

For those subjects who did not receive the treatment to which they were randomized (i.e., who erroneously received the wrong treatment at least once), an additional AE listing will be prepared displaying which events occurred after the treatment errors.

In addition for subjects who discontinue study treatment but continue with study participation, an additional AE listing will be prepared displaying which events occurred after the study treatment discontinuation.

### **2.8.1 Adverse events (AEs)**

The crude incidence of treatment emergent adverse events (TEAEs) (i.e., events started after the first dose of study treatment or events present prior to the first dose of study treatment but increased in severity based on preferred term and on or before last dose date + 84 days) will be summarized by primary system organ class and preferred term. Confidence intervals for the crude rate will be derived. In addition, exposure-adjusted incidence rates including 95% CI will be provided for the entire treatment period. A graphical display of the crude incidence rates and exposure-adjusted incidence rates will be presented for all AEs and serious AEs by system organ class.

Adverse events reported will be presented in descending frequency according to their incidence in total secukinumab group (combining all secukinumab treatment groups), starting from the most common event. Summaries (crude incidences only) will also be presented for AEs by severity and for study treatment-related AEs. If a particular AE 'severity' is missing, this variable will be listed as missing and treated as missing in summaries. If a subject reported more than one adverse event with the same preferred term, the adverse event with the greatest severity will be presented. If a subject reported more than one adverse event within the same primary system organ class, the subject will be counted only once with the greatest severity at the system organ class level, where applicable.

Separate summaries will be provided for adverse events suspected to be related to study drug, deaths, serious adverse events, adverse events leading to discontinuation, and adverse events leading to temporary dose interruption.

Adverse events will also be reported separately by SMQ according to MedDRA, using a narrow search. The MedDRA version used for reporting the study will be described in a footnote.

Non-treatment emergent adverse events will be listed.

For SAEs that occurred during screening, a listing will be prepared for all subjects screened including screening failures.

When adjudication is required of major cardiovascular events, a summary of those types of events as reported by the investigator and confirmed by adjudication will be provided.

An overview of the safety analyses which will be performed for treatment emergent AEs, on-treatment laboratory tests and vital signs for each analysis period is described below.

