5.5.5 Permitted dose adjustments and interruptions of study treatment

Study treatment dose adjustments are not permitted. Study treatment interruption is also not permitted with the following exceptions:

- Study treatment interruption is only permitted if, in the opinion of the investigator, a subject is deemed to be at a significant safety risk unless administration of investigational treatment is temporarily interrupted. In such cases study treatment should be interrupted only during the time that this risk is present and ongoing. Study treatment can be restarted at the next scheduled visit after resolution of the safety risk.
- The effect of secukinumab or adalimumab on live vaccines is unknown; therefore live vaccines should not be administered during participation in the study. The elimination of adalimumab may take up to four months (**Humira[®] SmPC**); in case a live vaccine has been administered due to a medical urgency, study treatment should be interrupted for four months for a subject taking GP2017. The study treatment should be interrupted for 12 weeks for a subject taking secukinumab.

Study treatment interruption or permanent discontinuation of study treatment will not affect the ability for the subject to remain in the study.

Any study treatment interruption must be recorded on the corresponding CRF.

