7.2.2 SAE reporting

To ensure subject safety, every SAE, regardless of causality, occurring after the patient has provided informed consent and until 20 weeks following the last administration of study treatment or until the end of study visit (whichever is later) must be reported to Novartis safety/CRO within 24 hours of learning of its occurrence. Any SAEs experienced after this period should only be reported to Novartis if the investigator suspects a causal relationship to study treatment.

All follow-up information for the SAE including information on complications, progression of the initial SAE and recurrent episodes must be reported as follow-up information to the original episode within 24 hours of the investigator receiving the follow-up information. An SAE occurring at a different time interval or otherwise considered completely unrelated to a previously reported one must be reported separately as a new event.

Information about all SAEs is collected and recorded on the Serious Adverse Event Report Form; all applicable sections of the form must be completed in order to provide a clinically thorough report. The investigator must assess the relationship of each SAE to each specific component of study treatment, (if study treatment consists of several components) complete the SAE Report Form in English, and submit the completed form within 24 hours to Novartis. Detailed instructions regarding the submission process and requirements for signature are to be found in the investigator folder provided to each site.

Follow-up information is submitted as instructed in the investigator folder. Each re-occurrence, complication, or progression of the original event must be reported as a follow-up to that event regardless of when it occurs. The follow-up information should describe whether the event has resolved or continues, if and how it was treated, whether the blind was broken or not, and whether the subject continued or withdrew from study participation.

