9.5.3 Safety variables

Adverse events

Treatment-emergent adverse events (events started after the first dose of study treatment or events present prior to the first dose of study treatment but increased in severity based on preferred term) will be summarized.

Adverse events will be summarized by presenting, for each treatment group, the number and percentage of subjects having any AE, having an AE in each primary system organ class and having each individual AE (preferred term). Summaries will also be presented for AEs by severity and for study treatment related AEs. If a subject reported more than one adverse event with the same preferred term, the adverse event with the greatest severity will be presented. If a subject reported more than one adverse event within the same primary system organ class, the subject will be counted only once with the greatest severity at the system organ class level, where applicable. Serious adverse events will also be summarized.

As appropriate, the incidence of AEs will be presented per 100 subject years of exposure.

[REDACTED]

Separate summaries will be provided for death, serious adverse event, other significant adverse events leading to discontinuation and adverse events leading to dose adjustment (including study treatment discontinuation).

A graphical display of relative frequencies within system organ classes and relative risks, as appropriate, will be presented.

[REDACTED]

Laboratory data

The summary of laboratory evaluations will be presented for three groups of laboratory tests (hematology and serum chemistry). Descriptive summary statistics for the change from baseline to each study visit will be presented. These descriptive summaries will be presented by test group, laboratory test and treatment group. Change from baseline will only be summarized for subjects with both baseline and post baseline.

For each parameter, the maximum change from baseline within each study period will be evaluated analogously.

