## 4 Change to protocol specified analyses

No change from protocol specified analysis was made.

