### 5.3 Visit Windows

When visit windows are used, all visits will be re-aligned, i.e., they will be mapped into one of the visit windows. E.g., if the Week 4 visit of a subject is delayed and occurs on Day 46 instead of on Day 29, it will be re-aligned to visit window Week 8. In the case of major deviations from the visit schedule, or due to unscheduled visits, several assessments of a subject may fall in a particular visit window (either scheduled or unscheduled). Statistical approaches to handle multiple assessments in a given visit window are specified below.

For laboratory and vital signs, follow-up (F/U) visit is excluded from analysis visit mapping window. Only assessments that come as F/U nominal visit will be directly assigned as analysis F/U visit. Other assessments that are beyond the last on-treatment visit window (W104) or after nominal F/U visit date won't be mapped to any analysis visit. F/U visit will not be included in the summary tables by visit.

Of note, subjects are allowed to have gaps in visits. All data collected will be displayed in listings.

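### The SAP ends treatment emergence 84 days after the last dose without declaring it, although the protocol sets no end date and collects SAEs for at least 140 days

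*SAP*

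**What the plan says.** Protocol 9.5.3 defines treatment-emergent events as "events started after the first dose of study treatment or events present prior to the first dose of study treatment but increased in severity" by preferred term. The definition ends there, with no closing date. SAP 2.8.1 repeats it and adds a limit: "increased in severity based on preferred term and on or before last dose date + 84 days". Under the same section, events that are not treatment-emergent are only listed. SAP Table 2-1, which holds the crude and exposure-adjusted incidences of AEs, SAEs and named risks, is introduced as covering treatment-emergent events.

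The 84-day limit recurs for exposure (SAP 2.4.1), laboratory data (2.8.2) and vital signs (2.8.3.1). SAP 5.3 adds, for laboratory data and vital signs, that the "F/U visit will not be included in the summary tables by visit". SAP section 4 states: "No change from protocol specified analysis was made".

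On collection, protocol 7.2.2 requires that every SAE, whatever its cause, occurring "until 20 weeks following the last administration of study treatment or until the end of study visit (whichever is later) must be reported" to the sponsor. Protocol 7.1 runs AE collection from consent to the end-of-study visit. On the comparator, protocol 5.5.5 says "The elimination of adalimumab may take up to four months"; sections 5.5.8 and 5.6.1 repeat this.

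**The concern.** Long-term safety is in the trial's title, and overall safety and tolerability is secondary objective 6. Protocol 3.6 names serious infections and malignancies among the most common SAEs with adalimumab. An event of that kind starting in the thirteenth week or later after the last dose must be reported to the sponsor within 24 hours, but it does not enter the Table 2-1 incidences. Those are the figures on which the arms would be compared.

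The narrowing is also undeclared. A reader who trusts SAP section 4 would take the tables to follow the protocol definition, and they do not. Concomitant medication shows the same pattern: protocol 9.3 runs it to the last study visit, SAP 2.4.2 stops it at 84 days, and section 4 is silent.

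**Working it through.** The 84 days are a rule, so the plan has no derived figure to reproduce. The check is window arithmetic.

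**Inputs.** Last planned dose: Week 100 for secukinumab, Week 102 for GP2017 (protocol 5.2). Cut-off: last dose + 84 days (SAP 2.8.1). SAE collection: the later of last dose + 20 weeks and the end-of-study visit, Week F120 (protocol 7.2.2). Planned size: 279 per arm (protocol 9.7).

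**Minimum gap for SAEs.** 20 × 7 = 140 days; 140 − 84 = 56 days, which is 56/140 = 40% of the 20-week post-dose period.

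**Treatment completers.**

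| | Secukinumab | GP2017 |
|---|---|---|
| Cut-off (last dose + 12 weeks) | Week 112 | Week 114 |
| SAE collection ends | Week 120 | Week 122 |
| SAE time collected, not counted | 8 weeks | 8 weeks |
| On-study time to F120, not counted | 8 weeks | 6 weeks |
| F112 after last dose | 84 days | 70 days |
| F120 after last dose | 140 days | 126 days |

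**Patient-years to F120 for completers.** With 80% completing, 0.80 × 279 ≈ 223 per arm.
- Secukinumab: 223 × 56 / 365.25 = 34.2.
- GP2017: 223 × 42 / 365.25 = 25.6.

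The 80% in protocol 9.7 joins two conditions: completing treatment and providing evaluable films at baseline and Week 104. The share completing treatment alone may therefore be higher. If all 279 completed, the figures would be 279 × 56 / 365.25 = 42.8 and 279 × 42 / 365.25 = 32.1.

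**Discontinuers who stay to F120.** Protocol section 6 encourages this. With last dose at Week L, the uncounted time is 120 − (L + 12) = 108 − L weeks: 84 weeks for L = 24, 56 for L = 52, 32 for L = 76. The total depends on when subjects stop and how long they stay, which the documents do not give.

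**GP2017 elimination.** Protocol 5.5.8 pairs four months with 16 weeks, or 112 days: 112 − 84 = 28 days. Four calendar months are 4 × 30.4375 = 121.75 days: 121.75 − 84 ≈ 38 days.

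**Laboratory data and vital signs.** Protocol Table 6-2 schedules haematology, chemistry and vital signs at F112 and F120, and protocol 9.5.3 plans change from baseline for every post-baseline visit. A completer's F120 values fall beyond day 84, so they leave the on-treatment summaries, and SAP 5.3 keeps both follow-up visits out of the by-visit tables. F112, if on schedule, falls inside the 84 days and can still enter the extreme-value and notable-value summaries.

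**Reading of the SAP sentence.** Taken literally, the limit could attach only to events that worsened. The identical limit for exposure, laboratory data and vital signs shows that it is meant for all treatment-emergent events.

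**The case against.** The strongest reply is that an SAP may refine a protocol definition, that one fixed post-dose window for both arms is orderly, and that a reporting rule for SAEs does not define an analysis window. Several parts of this stand.

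- A reader might infer that late SAEs disappear from the report. They do not. SAP 2.8.1 lists non-treatment-emergent events, SAP 2.8 adds a listing of events after treatment discontinuation, and the separate summaries of deaths and SAEs in 2.8.1 are not expressly confined to treatment-emergent events.
- A reader might infer that the exposure-adjusted rates are biased. SAP 2.4.1 ends exposure at the earlier of last dose + 84 days and the last visit, so numerator and denominator match.
- A reader might infer that the 84 days were set to one drug's washout. The protocol does use 12 weeks for secukinumab and 16 for GP2017 on live vaccines, but neither document gives that origin for the 84 days, and neither states an elimination time for secukinumab. The post-dose contraception examples are close: 20 weeks and 5 months.
- A reader might add up all discontinuers' later follow-up as lost. Most of that time lies far past any elimination figure in the protocol and may include other biologics, since protocol 5.5.6 lets subjects who start one remain in the study. It does not measure residual drug effect.

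What the reply does not answer is the conflict itself: the protocol definition has no end, the SAP's has one, and section 4 denies any change.

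**Conclusion.** The point holds as an undeclared shortening of the safety window. At least 56 days of collected SAE follow-up per subject fall outside every Table 2-1 incidence, assuming follow-up is not cut short by withdrawal of consent, loss or death. On GP2017 the cut-off comes 28 to about 38 days before the protocol's stated upper limit for elimination. For completers the excluded on-study time to F120 is about 34 patient-years on secukinumab and 26 on GP2017, on the assumption that 80% of 279 per arm complete treatment and are followed to F120.

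The extra time from discontinuers cannot be fixed from the documents. Nor can the number of events affected, because no late-event rate is given. The documents do not support a claim that the planned rates are biased or that late events go unreported. The SAP does leave open whether its separate death and SAE summaries extend past day 84.

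**What to change.** 1. Keep the 84-day tables as the on-treatment analysis.
2. Add a supplementary analysis by arm over the full collection period, with person-time to match: SAEs to the later of 20 weeks after last dose and the end-of-study visit, non-serious AEs to the end-of-study visit, plus deaths and named risks. The two collection limits differ, so each needs its own denominator.
3. State whether the separate death and SAE summaries in SAP 2.8.1 include events after day 84.
4. Add F112 and F120 to the laboratory and vital-sign visit summaries as off-treatment rows.
5. Record the 84-day rule in SAP section 4 as a change from protocol 9.5.3.

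The cost is SAP wording and a few tables on data already collected. The longer window dilutes on-drug rates and may include time on other treatments, which is why it should supplement the 84-day tables and not replace them.

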**Table 2-1 Overview of analyses on some safety endpoints**

Analysis period	AEs & SAEs	AEs by severity	Study drug related AEs	AEs-SMQ	Risk	Notables for vital signs and lab criteria
Entire Treatment	crude incidence exposure-adjusted incidence	crude incidence	crude incidence	crude incidence	crude incidence exposure-adjusted incidence	crude incidence

If adjudication is performed, the adjudication events (myocardial infarction, stroke, and cardiovascular death) will be listed.

Algorithms for date imputations will be provided in the Programming Datasets Specifications.

### 2.8.2 Laboratory data

The summary of laboratory data will only include on-treatment data, which are defined as those lab assessments after the first dose of study treatment and on or before the last dose + 84 days.

Reported laboratory assessments with either a less than or greater than sign (“<” or “>”) will be used for analysis after removal of the sign and conversion to standard units. These laboratory data will be displayed in listings using the standard units with the reported sign (“<” or “>”).

The summary of laboratory evaluations will be presented for three groups of laboratory tests (hematology, chemistry and urinalysis). In addition to the individual laboratory parameters, the ratios “total cholesterol / HDL” and “apolipoprotein B / apolipoprotein A1” will be derived and summarized.

For urinalysis, frequency tables will be presented.

Descriptive summary statistics for the change from baseline to each study visit will be presented. These descriptive summaries will be presented by laboratory test and treatment group. Change from baseline will only be summarized for subjects with both Baseline and post-Baseline values and will be calculated as:

$$\text{change from baseline} = \text{post-baseline value} - \text{baseline value}$$

For each parameter, the maximum change (maximum decrease and maximum increase) from baseline, if appropriate for each study phase, will be analyzed analogously.

In addition, shift tables will be provided for all parameters to compare a subject’s baseline laboratory evaluation relative to the visit’s observed value. For the shift tables, the normal laboratory ranges will be used to evaluate whether a particular laboratory test value was normal, low, or high for each visit, relative to whether or not the baseline value was normal, low, or high. If appropriate, the shifts to the most extreme laboratory test value within a treatment phase (either initial or entire) will be presented as well (including category “high and low”). These summaries will be presented by laboratory test and treatment group.

The following laboratory parameters will be analyzed with respect to numerical Common Terminology Criteria for Adverse Events (CTCAE) grades: hemoglobin, platelets, white blood cell count, neutrophils, lymphocytes, creatinine, total bilirubin (TBL), gamma-glutamyl

transferrase (GGT), alanine aminotransferase (ALT), aspartate aminotransferase (AST), alkaline phosphatase (ALP), glucose, cholesterol, triglycerides (TG).

These summaries will be split into hematology and chemistry for study level reports and the pooled summary of clinical safety.

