5.2 Treatment arms

Subjects will be randomly assigned at the baseline visit to one of the following three treatment groups in a 1:1:1 ratio, with approximately 279 randomized subjects planned for each group.

- Group 1: secukinumab 150 mg
- Group 2: secukinumab 300 mg
- Group 3: GP2017 (adalimumab biosimilar) 40 mg

Subjects in both of the secukinumab dose groups will receive study treatment at BSL, Weeks 1, 2, 3 and 4 followed by treatment every 4 weeks through Week 100. Subjects in the GP2017 group will receive study treatment at BSL and every two weeks through Week 102. Subjects can self-administer all secukinumab / placebo and GP2017 doses as described in [Section 3.1](#) at the study site or at home, according to the assessment schedule in [Table 6-1](#) and [Table 6-2](#).

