
S To be recorded in source document but not in CRF
 
Greyed visits are visits with at-home dosing, optional for on-site dosing
 
The BSL visit and randomization is Day 1
 
1 Eligibility and relevant medical history assessments are conducted at SV1, SV2 and BSL.
 
2 SI joint and spinal X-ray image acquisition must follow the vendor's Image Acquisition Guidelines. An SI joint X-ray taken within 3 months prior to SV1 may be utilized. The SI joint X-ray will be centrally read for eligibility.
 
3 Spinal X-rays (cervical + thoraco-lumbar) to be collected during the screening period to confirm eligibility for subjects with CRP < 5 mg/L. Subjects with CRP ≥ 5 mg/L and confirmed study eligibility should obtain the spinal X-rays at BSL.
 
4 Re-screening subjects may utilize previous X-rays if taken within the past 3 months according to the imaging criteria.
 
5 The PPD skin test can be performed at any time during the screening period, but it must be read within 72 hours and before randomization.
 
6 AS disease assessment includes: AS disease background, Modified New York criteria for AS and targeted medical history events related to AS.
 
7 A chest X-ray or MRI is required if it was not performed and evaluated within 3 months prior to screening. The X-ray should be performed after it is certain the subject meets inclusion/exclusion criteria in order to minimize unnecessary exposure to radiation. The X-ray may be replaced by an MRI assessment.
 
9 Sample must be obtained fasting.
 
10 MRI only performed in a sub-population of subjects at selected sites. All subjects at the selected MRI site should be considered for the MRI assessment.
 
11 AEs / SAEs occurring after the subject has signed the informed consent must be captured on the appropriate CRF.
 
For all subjects who discontinue from the study, the investigator should ensure that the subject completes the end of treatment visit (Week 104 visit assessments) 4 weeks after last study treatment of secukinumab or 2 weeks after last study treatment of GP2017, and also returns for the final follow-up visits, F112 and F120. Every attempt should be made to obtain the scheduled X-ray and MRI images at the final visit, unless the last X-ray and/or MRI were taken within 12 weeks before discontinuation.
 
** Hepatitis B and/or hepatitis C and/or HIV serology testing to be performed at local site during screening period, only if required per local medical practice or local regulations prior to initiation of therapy. These assessments will be documented in source records only and will not be entered into the CRF.
																																

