### 1.1 Study design

This multicenter study uses a randomized, partially-blinded, active-controlled, parallel-group design in subjects with AS. A screening period (SCR) of up to 10 weeks before randomization will be used to assess eligibility followed by 104 weeks of treatment. Two follow-up visits at Weeks 112 and 120 will occur thereafter.

At baseline (BSL), approximately 837 subjects whose eligibility is confirmed will be randomized to one of three treatment groups (1:1:1).

- Group 1: secukinumab 150 mg [1 x 1.0 mL s.c. plus placebo (1 x 1.0 mL s.c.)] at BSL, Weeks 1, 2 and 3, followed by administration every four weeks starting at Week 4
- Group 2: secukinumab 300 mg (2 x 1.0 mL s.c.) at BSL, Weeks 1, 2 and 3, followed by administration every four weeks starting at Week 4
- Group 3: GP2017 (adalimumab biosimilar) 40 mg (1 x 0.8 mL s.c.) at BSL followed by administration every two weeks starting at Week 2

Although study treatment (secukinumab vs GP2017) will be provided in an open-label fashion to the subjects, secukinumab study treatment will be blinded to the dose. Subjects in groups 1 and 2 will know that they are on secukinumab, but will be blinded to which treatment group and will not know whether they are receiving secukinumab 150 mg or 300 mg. Subjects in the GP2017 treatment group will know that they are receiving GP2017 (adalimumab biosimilar) 40 mg. Investigators and study site staff will be blinded in the same manner.

The primary endpoint analysis may be performed after all subjects complete the assessments associated with the primary endpoint visit (Week 104) in order to support regulatory filing. The final analysis will be conducted after all subjects complete the study at Week F120.

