## 2.8.3 Other safety data

### 2.8.3.1 Vital signs

The summary of vital signs will only include on-treatment data, which are defined as those vital sign measurements after the first dose of study treatment and on or before last dose + 84 days.

Analysis in vital sign measurement using descriptive summary statistics for the change from baseline for each post-baseline visit will be performed. These descriptive summaries will be presented by vital sign and treatment group. Change from baseline will only be summarized for subjects with both baseline and post-baseline values and will be calculated as:

$$\text{change from baseline} = \text{post-baseline value} - \text{baseline value}$$

The number and percentage of subjects with newly occurring notable vital signs will be presented. Criteria for notable vital sign abnormalities are provided below:

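### The SAP's last dose + 84 days limit for labs and vital signs leaves F112 no slack on secukinumab and 14 days on GP2017, so late F112 values are handled differently by arm in entire-treatment summaries

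*SAP*

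**What the plan says.** **Cut-off.** SAP 2.8.2 counts as on-treatment "those lab assessments after the first dose of study treatment and on or before the last dose + 84 days". SAP 2.8.3.1 uses the same limit: "those vital sign measurements after the first dose of study treatment and on or before last dose + 84 days". Both limits are inclusive and apply to every arm.

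**Dosing.** Under Protocol 5.2 both secukinumab arms are dosed at baseline, "Weeks 1, 2, 3 and 4 followed by treatment every 4 weeks through Week 100". For the comparator: "Subjects in the GP2017 group will receive study treatment at BSL and every two weeks through Week 102".

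**Follow-up.** SAP 1.1: "Two follow-up visits at Weeks 112 and 120 will occur thereafter". Protocol Table 6-2 schedules hematology, chemistry, lipids and vital signs at both visits. Protocol section 6 gives no numerical visit tolerance; it asks for the designated day or as near to it as can be managed.

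**Visit mapping.** SAP 5.3 keeps follow-up labs and vital signs out of the analysis visit windows, assigns nominal follow-up samples to their own follow-up visit, and adds that "F/U visit will not be included in the summary tables by visit".

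**Summaries not organised by visit.** SAP Table 2-1 reports lab and vital-sign notables over the entire treatment period as crude incidence only. SAP 2.8.2 also plans maximum change, most extreme shift, worst CTCAE grade over the treatment phase, and newly occurring or worsening lipid and liver abnormalities. SAP Table 5-4 takes notables as the most extreme measurement within a window.

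**The concern.** A limit counted from the last dose, applied to follow-up visits at fixed calendar weeks, treats arms differently when their last doses fall two weeks apart. On secukinumab, an F112 sample taken one day late (with the last dose on schedule) falls outside the rule. On GP2017 the same sample stays inside until it is more than 14 days late.

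This matters only where a subject's worst value over the whole period is used. In such a summary an additional sample can add a case but never remove one, and Table 2-1 plans no exposure-adjusted rate for labs or vital signs. Any imbalance would raise GP2017 relative to secukinumab, in tables that serve the secondary safety objective. Whether a secukinumab off-drug sample is included would also turn on a single day of scheduling.

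**Working it through.** **1. Day numbering.** The Table 6-1 footnotes state that "The BSL visit and randomization is Day 1", so Day = 7 × week + 1. This gives Week 100 = 701 and Week 104 = 729, matching the target days in SAP Table 5-3. Hence Week 102 = 715, F112 = 785 and F120 = 841.

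**2. Cut-offs for a subject dosed on schedule.**

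| | Last dose | + 84 days | Slack at F112 (785) | Relative to F120 (841) |
|---|---|---|---|---|
| Secukinumab | 701 | 785 | 0 days | 56 days short |
| GP2017 | 715 | 799 | 14 days | 42 days short |

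F120 is outside the limit in every arm. Early stoppers have their final visit 4 weeks (secukinumab) or 2 weeks (GP2017) after the last dose. If F112 is then held 8 weeks later (an assumption), it falls 28 + 56 = 84 or 14 + 56 = 70 days after the last dose, which is the same offset.

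**3. Share of F112 samples falling after the limit.** The documents give no distribution of visit dates. Assume the last dose is on schedule and the F112 date is normal around its target with mean shift m and standard deviation SD, in whole days. Then share lost = 1 − Φ((slack + 0.5 − m)/SD).

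| Assumption | Secukinumab | GP2017 |
|---|---|---|
| All visits on target | 0% | 0% |
| m = 0, SD 1 | 31% | 0% |
| m = 0, SD 3 | 43% | 0% |
| m = 0, SD 7 | 47% | 2% |
| m = 0, SD 10 | 48% | 7% |
| m = 3 days early, SD 3 | 12% | 0% |
| m = 3 days late, SD 3 | 80% | 0% |

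**4. Effect on ever-abnormal incidence if F112 is used.** SAP Table 5-3, Group 1, has 10 post-baseline analysis visits through Week 104 (Weeks 4, 12, 16, 24, 40, 52, 64, 76, 92, 104). Let q be the assumed chance of a notable value per visit and f the between-arm difference in the share of F112 samples counted. With no true difference and independent visits, the excess on GP2017 is f × q × (1 − q)^10. Take f = 0.45 (symmetric scatter, SD about 3 to 7 days):

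- q = 1%: 0.45 × 0.01 × 0.904 = 0.4 points
- q = 5%: 0.45 × 0.05 × 0.599 = 1.3 points

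Repeated values in one person are correlated, and a subject already flagged cannot be counted again. With an assumed latent within-subject correlation of 0.5 to 0.8, the excess falls to 0.20-0.08 points (q = 1%) and 0.55-0.23 points (q = 5%). All these figures scale in proportion to f.

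Lipids are drawn only at Weeks 52 and 104 before F112, so F112 weighs more. With independence and f = 0.45, the excess is 0.45 × 0.01 × 0.99² = 0.4 points at 1% and 0.45 × 0.05 × 0.95² = 2.0 points at 5%. Correlation reduces these too.

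**5. Which summaries are exposed.** SAP 5.3 settles the by-visit tables, since follow-up is out in all arms. For worst grade, most extreme shift, maximum change, and lipid and liver abnormalities, the explicit inclusion rule is the 84-day definition. For notables the SAP points both ways: 2.8.2 and 2.8.3.1 would admit an F112 value inside 84 days, while Table 5-4 works within windows from which 5.3 has removed follow-up.

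**The case against.** The strongest reply is that SAP 5.3 already places nominal follow-up outside the on-treatment windows, and Table 5-4 draws notables from windows, so no arm gains a look there. Protocol Table 6-2 also labels F112 as follow-up rather than treatment. For notables this is a fair reading, but it conflicts with 2.8.2 and 2.8.3.1. It does not reach the worst-grade, maximum-change, lipid and liver summaries, for which Table 5-4 gives no rule of that kind.

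A second reply is that equal follow-up after the last dose is principled and matches the SAP's adverse-event rule. GP2017's later limit reflects two more weeks of dosing (798 versus 784 days, or 1.8% longer). That holds for adverse events, whose onset can fall on any day. It fits poorly where data exist only at scheduled visits and the limit lands exactly on one of them.

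Third, a cut at Week 104 has its own asymmetry: that visit is 28 days after the last secukinumab dose and 14 days after the last GP2017 dose. This bears on where to cut, not on whether one visit rule should apply to all arms.

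A reader might also infer that GP2017 simply gets an additional counted visit, or that about half of secukinumab completers lose F112. The documents support neither. The limit is inclusive, so an on-schedule F112 counts in every arm. Any share lost comes from assumed visit scatter, and a late last dose followed by an equally late F112 loses nothing.

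**Conclusion.** The slack of 0 versus 14 days at F112 is exact and follows from the documents alone. It makes inclusion of late F112 labs and vital signs depend on arm, but only in the entire-treatment worst-value and notable summaries; for notables the SAP needs to resolve its own inconsistency first. By-visit tables and efficacy are untouched.

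The size is conditional. Under symmetric scatter, roughly 30-48% of secukinumab F112 samples would be lost, and none if all visits are on target. The spurious excess on GP2017 is then about 0.1 to 1.3 percentage points for the ten-visit panels at assumed notable rates of 1-5% per visit. For lipids it could reach 2.0 points if visits were independent. For comparison, the standard error of a difference between two arms of 279 on the ten-visit outcomes, with F112 as an eleventh look, is about 2.6 to 4.2 points (√(2p(1 − p)/279), p = 1 − (1 − q)^11). A reader might conclude that the safety comparison is materially biased toward secukinumab. The documents do not support that: these tables are descriptive, lie outside the testing strategy, and show an effect of this size only under assumed visit scatter and only if F112 values are used. The point is still worth correcting, because the asymmetry follows from the stated rule and is easy to remove.

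**What to change.** In SAP 2.8.2 and 2.8.3.1, and consistently in 5.3 and Table 5-4, state that nominal F112 lab and vital-sign values are handled identically in every arm for the entire-treatment worst-value and notable summaries. Either include nominal F112 in all arms, or exclude it in all arms and report F112 and F120 separately as follow-up. Say the same for early stoppers. Keep last dose + 84 days for adverse events.

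The cost is a few sentences of SAP text and a flag in two analysis datasets, with no new data. The small downside is that the lab and vital-sign rule then differs slightly from the adverse-event rule, which a table footnote can explain.
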